1.3. Potential Risks and Benefits of the Treatment Regimen

1.3.1. INCB039110

As of 13 DEC 2016, 9 Phase 1, 4 Phase 1/2, and 5 Phase 2 clinical studies with INCB039110, including studies of INCB039110 in combination with chemotherapeutic agents, corticosteroids, pembrolizumab (anti-programmed cell death 1 monoclonal antibody), and investigational PI3K δ (INCB040093 and INCB050465) and indoleamine 2,3-dioxygenase 1 (epacadostat) inhibitors, have either been completed or are ongoing. A total of 777 subjects were enrolled in these studies and received at least 1 dose of INCB039110. In completed clinical pharmacology studies, INCB039110 has been administered to 197 healthy adult subjects as a single dose, repeat single doses, or multiple doses for up to 10 days.

In the ongoing and completed clinical pharmacology studies, INCB039110 was generally safe and well tolerated in healthy subjects, with few discontinuations. The majority of treatment-emergent adverse events (TEAEs) were mild in severity. There have been no clinically significant, unanticipated safety findings or trends observed. The main drug effect identified was a rapidly reversible dose related decrease in neutrophil counts presumably caused by neutrophil margination; neutrophil decreases generally resolved within 24 to 48 hours of dose discontinuation. Other reversible hematologic abnormalities, including decreased reticulocyte count, were observed after multiple-dose administration of higher dose levels at which JAK2 inhibition was noted.

Adverse events (AEs) that have been reported by more than 5% of healthy subjects in an individual study receiving INCB039110 included fatigue, headache, neutropenia, nausea, contact dermatitis, ecchymosis, reticulocyte count decreased, excoriation, and nasal congestion. Adverse events reported by more than 10% of subjects receiving INCB039110 in the psoriasis study included nasopharyngitis. Adverse events reported by more than 10% of subjects in the MF study included fatigue, thrombocytopenia, nausea, diarrhea, upper respiratory tract infection, constipation, cough, dyspnea, peripheral edema, pyrexia, dizziness, abdominal pain, night sweats, pain in extremity, arthralgia, contusion, headache, pruritus, vomiting, and increased bilirubin/hyperbilirubinemia. In the RA study, there were no TEAEs reported by more than 10% of subjects.

Events reported in ≥ 5 subjects in any study in which INCB039110 was given in conjunction with chemotherapy were as follows: anemia, fatigue, thrombocytopenia, nausea, pyrexia, neutropenia, diarrhea, dysgeusia, peripheral edema, headache, alopecia, cough, dyspnea, constipation, decreased appetite, epistaxis, vomiting, and hypoalbuminemia.

In lymphoid malignancies where INCB039110 was given in combination with INCB040093, a PI3K δ inhibitor (N = 71), TEAEs observed in $\geq 10\%$ of subjects included nausea, cough, diarrhea, pyrexia, thrombocytopenia/platelet count decreased, vomiting, fatigue, neutropenia/neutrophil count decreased, chills, night sweats, aspartate aminotransferase increased, constipation, decreased appetite, headache, back pain, dyspnea, oropharyngeal pain, rash, alanine aminotransferase (ALT) increased, abdominal pain, anemia, asthenia, blood cholesterol increased, leukocytosis, upper respiratory tract infection, peripheral edema, dizziness, and pain in extremity. Serious AEs reported in more than 1 subject included *Pneumocystis jirovecii* pneumonia (5 subjects), pyrexia (5 subjects), pneumonia (3 subjects), urinary tract infection (3 subjects), cardiac arrest (2 subjects), and respiratory failure (2 subjects).

Because of the potential for myelosuppression, subjects will have hematologic parameters closely monitored during clinical studies. If there are clinically relevant declines in hematology parameters, therapy may be interrupted until resolution or discontinuation. As INCB039110 also has the potential to cause white blood cell (WBC) margination (ie, a transient decrease in absolute neutrophil count [ANC]), assessment of hematology parameters should be performed before study drug administration at all applicable study visits.

Results from each of these studies are summarized in the [INCB039110 IB](#).

1.3.2. Ibrutinib

1.3.2.1. Summary of Clinical Safety

Pooled safety data for a total of 423 subjects treated with various therapies in combination with ibrutinib from 4 studies conducted in B-cell malignancies, which included 1 randomized control study, are summarized in [Table 2](#). Therapies used in combination with ibrutinib in these studies, included BR (bendamustine and rituximab), FCR (fludarabine, cyclophosphamide, and rituximab), ofatumumab, and R-CHOP.

Table 2: Most Frequently Reported TEAEs in Subjects Receiving Ibrutinib in Combination Therapy (N = 423)

Most Frequently Reported TEAEs > 10%	Most Frequently Reported Grade 3 or 4 TEAEs > 2%	Most Frequently Reported Serious TEAEs > 1%
Neutropenia	Neutropenia	Febrile neutropenia
Diarrhea	Thrombocytopenia	Pneumonia
Nausea	Febrile neutropenia	Atrial fibrillation
Thrombocytopenia	Pneumonia	Pyrexia
Fatigue	Hypertension	

For more detailed information, refer to the current version of the [ibrutinib IB](#).

1.3.2.2. Risks

1.3.2.2.1. Bleeding-Related Events

There have been reports of hemorrhagic events in subjects treated with ibrutinib, both with and without thrombocytopenia. These include minor hemorrhagic events, such as contusion, epistaxis, and petechiae, and major hemorrhagic events, some fatal, including gastrointestinal bleeding, intracranial hemorrhage, and hematuria. Use of ibrutinib in subjects requiring other anticoagulants or medications that inhibit platelet function may increase the risk of bleeding. Subjects with congenital bleeding diathesis have not been studied. See Section 5.7 for guidance on concomitant use of anticoagulants, antiplatelet therapy, and/or supplements. See Section 5.8 for guidance on ibrutinib management with surgeries or procedures.

1.3.2.2.2. Infections

Fatal and nonfatal infections have occurred with ibrutinib therapy. At least 25% of subjects with MCL and 35% of subjects with CLL had Grade 3 or greater infections per NCI CTCAE v4.03 (NCI 2010). The most commonly reported infections include pneumonia, cellulitis, urinary tract infection, and sepsis. Although causality has not been established, cases of progressive multifocal leukoencephalopathy have occurred in patients treated with ibrutinib.

1.3.2.3. Cytopenias

Treatment-emergent Grade 3 or 4 cytopenias (neutropenia, thrombocytopenia, and anemia) were reported in subjects treated with ibrutinib.

1.3.2.4. Atrial Fibrillation

Atrial fibrillation and atrial flutter have been reported in subjects treated with ibrutinib, particularly in subjects with cardiac risk factors, acute infections, and a previous history of atrial fibrillation. For atrial fibrillation that persists, the risks and benefits of ibrutinib treatment should be considered, and the Protocol dose modification guidelines should be followed (see Section 5.5.1.2).

1.3.2.5. Second Primary Malignancies

Second primary malignancies, most frequently skin cancers, have occurred in subjects treated with ibrutinib. Second primary malignancies, including nonskin carcinomas (SCC and BCC), have occurred in patients treated with ibrutinib. The most frequent second primary malignancy was non-melanoma skin cancer.

1.3.2.6. Tumor Lysis Syndrome

There have been reports of tumor lysis syndrome events in subjects treated with single-agent ibrutinib or in combination with chemotherapy. Subjects at risk of tumor lysis syndrome are those with comorbidities and/or risk factors, such as high tumor burden before treatment, increased uric acid (hyperuricemia), elevated LDH, bulky disease at baseline, and pre-existing kidney abnormalities.

1.3.2.7. Diarrhea

Diarrhea is the most frequently reported nonhematologic AE with ibrutinib monotherapy and combination therapy. Other frequently reported gastrointestinal events include nausea, vomiting, and constipation. These events are rarely severe. Should symptoms be severe or prolonged follow the Protocol dose modification guidelines (see Section 5.5.1.2).

1.3.2.8. Rash

Rash has been commonly reported in subjects treated with either single-agent ibrutinib or in combination with chemotherapy. In a randomized Phase 3 study, rash occurred at a higher rate in the ibrutinib group than in the control group. Most rashes were mild to moderate in severity.

1.3.2.9. Interstitial Lung Disease

Cases of interstitial lung disease (ILD) have been reported in subjects treated with ibrutinib. Randomized, controlled Phase 3 studies did not show an increased incidence rate of ILD in subjects treated with ibrutinib as compared to subjects treated with active control. Subjects should be monitored and evaluated for symptoms (eg, dyspnea, cough or pyrexia) and treated symptomatically, including interruption of the suspected agent as appropriate.

1.3.3. Potential Risks and Benefits for the Combination of INCB039110 and Ibrutinib

Treatment-emergent cytopenias have been reported with INCB039110 monotherapy and ibrutinib monotherapy; it is not known whether the combination of INCB039110 and ibrutinib would precipitate more frequent, more severe, and/or new cytopenias (or other toxicities) or risk for infections as compared with each agent individually. Both INCB039110 and ibrutinib are primarily metabolized in the liver by cytochrome P450 (CYP) 3A4; [REDACTED].

The combination of INCB039110 and ibrutinib is being tested for the first time in this clinical study and, therefore, any potential benefit is hypothesized based on preclinical studies. As described in Section 1.2.4, preclinical data suggest that both the JAK/STAT and BTK pathways may contribute to driving tumor growth and survival in DLBCL, and combination therapies that block both pathways may prove more beneficial in these diseases due to the central role that JAK-mediated cytokine signaling plays in augmenting BCR-mediated activation of the NF- κ B pathway.

2. STUDY OBJECTIVES AND ENDPOINTS

2.1. Study Objectives

2.1.1. Phase 1

2.1.1.1. Primary Objective

The primary objective of Phase 1 is to evaluate the safety and tolerability of INCB039110 in combination with ibrutinib in subjects with relapsed or refractory DLBCL).

2.1.1.2. Secondary Objective

The secondary objective of Phase 1 is to evaluate the efficacy of INCB039110 in combination with ibrutinib in terms of ORR.

[REDACTED]

2.1.2. Phase 2

2.1.2.1. Primary Objective

The primary objective of Phase 2 is to evaluate the efficacy of INCB039110 in combination with ibrutinib in subjects with relapsed or refractory non-GCB DLBCL as demonstrated by ORR.

2.1.2.2. Secondary Objectives

The secondary objectives of Phase 2 are as follows:

- To evaluate efficacy in terms of duration of response (DOR), durable response rate, and PFS.
- To evaluate the safety and tolerability of the treatment combination.

[REDACTED]

2.2. Study Endpoints

2.2.1. Phase 1

Efficacy endpoints will be assessed using the Lugano Classification ([Cheson et al 2014](#)); AEs will be assessed using NCI CTCAE v4.03 ([NCI 2010](#)).

2.2.1.1. Primary Endpoint

Safety and tolerability will be assessed by evaluating the frequency, duration, and severity of AEs (including SAEs and dose-limiting toxicities [DLTs]) and changes in clinical and laboratory assessments.

2.2.1.2. Secondary Endpoint

Efficacy will be assessed by ORR, defined as the percentage of subjects achieving either a CR or PR.

[REDACTED]

2.2.2. Phase 2

2.2.2.1. Primary Endpoint

Efficacy will be assessed by ORR, defined as the percentage of subjects achieving either a CR or PR.

2.2.2.2. Secondary Endpoints

- DOR, defined as the time from earliest date of disease response until earliest date of disease progression.
- Durable response rate, defined as the percentage of subjects achieving a CR or PR for > 16 weeks.
- PFS, defined as the time from enrollment until the earliest date of disease progression determined by objective radiographic disease assessments, or death due to any cause.
- Safety and tolerability via assessment of the frequency, duration, and severity of AEs and SAEs, and changes in clinical and laboratory assessments.

3. SUBJECT ELIGIBILITY

Deviations from eligibility criteria are not allowed because they can potentially jeopardize the scientific integrity of the study, regulatory acceptability, and/or subject safety. Therefore, adherence to the criteria as specified in the Protocol is essential.

3.1. Subject Inclusion Criteria

The following criteria are required for inclusion in the study:

1. Male or female, 18 years of age or older.
2. Histologically documented diagnosis of *de novo* DLBCL.
 - a. For Phase 1, subjects may have any DLBCL subtype.
 - b. For Phase 2, subjects must have ABC or unclassifiable subtypes of DLBCL confirmed by immunohistochemistry (IHC) using the Hans algorithm.

Subjects having a computed tomography (CT) scan abnormality with uncertain interpretation following completion of the most recent treatment regimen must have biopsy confirmation of residual DLBCL before study entry.

3. Relapsed or refractory DLBCL, defined as having received at least 1 but no more than 3 prior treatment regimens and ineligible for HDC/ASCT.
4. Fluorodeoxyglucose-avid disease (based on local evaluation) per the Lugano Classification ([Cheson et al 2014](#)). Fluorodeoxyglucose-avid disease is defined as disease with a 5-point scale (5PS) score of 4 or 5.
5. Subjects must have archived tumor tissue (block or 15-20 unstained slides) available, or be willing to undergo an incisional or excisional lymph node biopsy of accessible adenopathy (or, in less accessible lymph nodes, 4 to 8 core biopsies).
6. At least 1 measurable (≥ 2 cm in longest dimension) lesion on CT scan or magnetic resonance imaging (MRI).
7. Eastern Cooperative Oncology Group (ECOG) performance status 0 to 2.
8. Adequate bone marrow, renal, and hepatic function, per local reference laboratory ranges (values must not be achieved with growth factors) as follows:
 - a. ANC $\geq 1.5 \times 10^9/L$.
 - b. Platelet count $\geq 75 \times 10^9/L$.
 - c. Hemoglobin ≥ 8.0 g/dL (transfusions are permitted to achieve required hemoglobin level).
 - d. Serum creatinine ≤ 2.0 g/dL or measured or calculated creatinine clearance ≥ 30 mL/min by the Cockcroft-Gault Equation.

- e. Aspartate aminotransferase (AST) and ALT $\leq 2.5 \times$ institutional upper limit of normal (ULN) or $\leq 5 \times$ ULN for subjects with known hepatic metastases.
 - f. Total bilirubin $\leq 1.5 \times$ ULN if no liver metastases or $< 3 \times$ ULN in the presence of liver metastases or presence of documented Gilbert's syndrome (unconjugated hyperbilirubinemia). Further evaluation should be performed to confirm and document the origin of increase.
9. Prothrombin time (PT)/international normalized ratio (INR) $< 1.5 \times$ ULN and activated partial thromboplastin time (aPTT) $< 1.5 \times$ ULN.
10. Willingness to avoid pregnancy or fathering children based on the criteria below:
- a. Woman of nonchildbearing potential (ie, surgically sterile with a hysterectomy and/or bilateral oophorectomy OR ≥ 12 months of amenorrhea).
 - b. Woman of childbearing potential who has a negative serum pregnancy test at screening and before the first dose on Day 1 and who agrees to take appropriate precautions to avoid pregnancy (with at least 99% certainty) from screening through up to 3 months after ending treatment. Permitted methods that are at least 99% effective in preventing pregnancy (see [Appendix A](#)) should be communicated to the subject and their understanding confirmed.
 - c. Man who agrees to take appropriate precautions to avoid fathering children (with at least 99% certainty) from screening through up to 3 months after ending treatment. Permitted methods that are at least 99% effective in preventing pregnancy (see [Appendix A](#)) should be communicated to the subject and their understanding confirmed.
11. Ability to comprehend and willingness to sign an informed consent form (ICF).

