3.2. Subject Exclusion Criteria

If met, any of the following criteria will lead to subject exclusion from the study:

1. Transformed DLBCL or DLBCL with coexistent histologies (eg, follicular or mucosa-associated lymphoid tissue lymphoma).
2. PMBL.
3. Known CNS lymphoma (either primary or metastatic).
4. Autologous stem cell transplant within the previous 3 months, allogeneic stem cell transplant within the previous 6 months, or active graft versus host disease following allogeneic transplant.
5. Use of immunosuppressive therapy within 28 days of starting study treatment. Immunosuppressive therapy includes, but is not limited to, cyclosporine A, tacrolimus, or high-dose corticosteroids. Subjects receiving corticosteroids must be at a dose level ≤ 10 mg/day within 7 days of initiating study treatment.
6. Prior or concurrent therapy with a JAK inhibitor or BTK inhibitor.

7. Receipt of anticancer medications or investigational drugs within the following intervals before starting study treatment (unless otherwise approved by the sponsor):
 - a. < 6 weeks for mitomycin-C or nitrosoureas.
 - b. < 28 days for any investigational agent for any indication.
 - c. < 21 days or 5 half-lives (whichever is greater) for all other cytotoxic anticancer medications.
 - d. < 4 weeks for monoclonal antibodies used as anticancer treatment.
 - e. < 10 weeks or 5 half-lives from completion of any radio- or toxin-immunoconjugates.
8. Major surgery 28 days before starting study treatment.
9. Prior treatment-related toxicities that have not resolved to \leq Grade 1, with the exception of Grade \leq 2 neuropathy and any grade of alopecia.
10. Chronic or current active infectious disease requiring systemic antibiotics, antifungal, or antiviral treatment.
11. Clinically significant cardiac disease, including unstable angina, acute myocardial infarction, and/or cardiac conduction issues within 6 months of Day 1; New York Heart Association Class II to IV congestive heart failure; or uncontrolled arrhythmia.
12. Known bleeding disorders (eg, von Willebrand's disease) or hemophilia.
13. History of stroke or intracranial hemorrhage within 6 months before study entry.
14. Significant concurrent, uncontrolled medical condition including, but not limited to, renal, hepatic, hematological, gastrointestinal, endocrine, pulmonary, neurological, cerebral, or psychiatric disease.

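### Inclusion criterion 8d gives the serum creatinine limit in g/dL, so on its own it sets no effective numeric renal limit

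*Protocol*

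**What the plan says.** Criterion 8 in Protocol Section 3.1 opens with "Adequate bone marrow, renal, and hepatic function, per local reference laboratory ranges (values must not be achieved with growth factors) as follows". The renal item beneath it, 8d, is "Serum creatinine ≤ 2.0 g/dL or measured or calculated creatinine clearance ≥ 30 mL/min", with Cockcroft-Gault named as the equation. The key inclusion criteria in the synopsis repeat the item with the same unit. The item just above it, 8c, is the hemoglobin requirement, "Hemoglobin ≥ 8.0 g/dL (transfusions are permitted to achieve required hemoglobin level", where g/dL is the expected unit.

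No other part of the protocol gives the creatinine limit in another unit, and the SAP does not restate it. Section 3 opens with the rule that "Deviations from eligibility criteria are not allowed because they can potentially jeopardize the scientific integrity of the study, regulatory acceptability, and/or subject safety".

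Renal disease also appears in exclusion 14 (Section 3.2), which covers "Significant concurrent, uncontrolled medical condition including, but not limited to, renal, hepatic, hematological" and other organ systems. Exclusion 23 covers any condition that would endanger the subject or compromise compliance. Neither carries a number.

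Protocol Section 9.1 and SAP Section 5.3.2 admit a subject to the per-protocol population only if all inclusion and exclusion criteria were met.

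**The concern.** A serum creatinine limit of 2.0 g/dL is too high to separate any subject from any other. Because the two limbs are alternatives, a limb that is always met makes the other irrelevant, and the stated clearance of 30 mL/min does no work.

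Two things are at stake. First, the one numeric renal safeguard at entry is not functioning as written, in a protocol that forbids deviations from its criteria. A site that reads the unit literally and a site that silently reads mg/dL are applying different rules, and only the literal one matches the approved text. Second, whether a subject met criterion 8d, and so can belong to the per-protocol population, depends on which unit is used.

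**Working it through.** **Inputs.** From criterion 8d: creatinine limit 2.0 g/dL; clearance limit 30 mL/min; connective *or*; Cockcroft-Gault named as the equation. The documents do not print the equation, so I take its usual form: CrCl (mL/min) = (140 − age) × weight in kg / (72 × creatinine in mg/dL), multiplied by 0.85 for women. The ages, weights and creatinine values below are assumed for illustration.

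**Step 1: the unit.** 2.0 g/dL × 1000 mg/g = 2000 mg/dL. The main conclusion rests on this conversion; the clearance figures only show scale.

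**Step 2: are the two limbs of similar strictness as written?** Clearance at a creatinine of 2000 mg/dL:

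- Man, 20 y, 120 kg: 120 × 120 / (72 × 2000) = 0.10 mL/min.
- Man, 60 y, 70 kg: 80 × 70 / (72 × 2000) = 0.039 mL/min.
- Woman, 85 y, 50 kg: 55 × 50 × 0.85 / (72 × 2000) = 0.016 mL/min.

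Against 30 mL/min, the creatinine limb is looser by a factor of 30 / 0.10 = 300 to 30 / 0.0162 ≈ 1,850. The two limits in one sentence cannot both describe adequate renal function.

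**Step 3: who passes 8d?** Assumed man, 60 y, 70 kg, so CrCl = 5600 / (72 × creatinine):

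| Creatinine (mg/dL) | CrCl (mL/min) | 8d as written | 8d if the unit were mg/dL |
|---|---|---|---|
| 2 | 38.9 | pass | pass |
| 2.5 | 31.1 | pass | pass |
| 4 | 19.4 | pass | fail |
| 8 | 9.7 | pass | fail |
| 15 | 5.2 | pass | fail |
| 30 | 2.6 | pass | fail |

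Even at 30 mg/dL the creatinine is 0.03 g/dL, far below 2.0 g/dL. As written, the criterion separates nobody.

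**Step 4: does mg/dL make the sentence coherent?** At 2.0 mg/dL the clearance is 5600 / 144 = 38.9 mL/min for the same man, and 38.9 × 0.85 = 33.1 mL/min for a woman of the same age and weight. Across the assumed extremes it runs from 16 mL/min (woman, 85 y, 50 kg) to 100 mL/min (man, 20 y, 120 kg). That is the same order as the 30 mL/min alternative, which is why mg/dL appears to be meant. The documents do not confirm it.

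**Step 5: would the unit alone make 30 mL/min a floor?** No. For an assumed woman of 75 y and 60 kg at 2.0 mg/dL, CrCl = 65 × 60 × 0.85 / (72 × 2.0) = 23.0 mL/min. She passes on the creatinine limb although her clearance is below 30. Under *or*, a subject fails only if both limbs fail.

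**Step 6: where does it reach the analysis?** SAP Sections 5.1 and 5.3.1 assign all Phase 2 efficacy analyses to the intent-to-treat population, which does not depend on the criteria having been met. SAP Section 5.3.2 reserves the per-protocol population for supportive sensitivity analyses, and SAP Appendix B lists one per-protocol efficacy table, 2.1.2. No sample-size, power or boundary calculation uses the creatinine limit.

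**The case against.** The strongest reply is that this is an obvious slip, perhaps carried down from the hemoglobin line, and that sites will read mg/dL because no other reading fits a requirement for adequate renal function. That is probably how it works in practice, and it limits the seriousness. It does not remove the need to correct the text. The limit is an operative eligibility threshold, it stands in two places, and the protocol says its criteria must be followed as specified. Appendix C shows that the neighboring items 8e and 8f were revised in Amendments 2 and 3, yet the unit remains in Version 5.

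A second reply is that other criteria screen for renal disease. This stands in part. A reader might infer from the broken limit that a subject with severe renal impairment is simply eligible and that enrolling one would not be a deviation. The documents do not support that. Eligibility requires every inclusion and no exclusion, and exclusion 14 (renal disease named) or exclusion 23 could rule such a subject out. Exclusion 9 could also apply where renal toxicity from earlier treatment has not resolved. These criteria rest on judgment, though. Stable, controlled impairment might not meet exclusion 14, so they do not replace a numeric limit.

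A third reply is that the effect on the results is small. That stands: the primary analysis and the Simon rule do not depend on this criterion.

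**Conclusion.** Wrong as written. The creatinine limit is 1000 times too large if mg/dL was meant. Whatever was meant, the printed unit makes the creatinine limb always true and the clearance limb idle. Criterion 8d alone sets no effective numeric renal limit, contrary to its own lead-in.

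The consequence is bounded. Exclusions 14 and 23 remain, and the analysis effect is confined to membership of the supportive per-protocol population. A reader might go further and infer that unsuitable subjects were enrolled, or that the response-rate test is compromised. Nothing in the documents shows the first, and the intent-to-treat basis of the efficacy analyses rules out the second as a consequence of this wording. How many subjects would change status under mg/dL cannot be computed from the documents.

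The unit conversion and the effect of *or* need no assumption beyond the fact that no subject has a creatinine near 2000 mg/dL. That mg/dL was intended is an inference for the sponsor to confirm.

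**What to change.** 1. The sponsor confirms the intended unit; mg/dL appears intended.
2. The unit is corrected in Section 3.1 (criterion 8d) and in the synopsis together, and in any eligibility check that was programmed from the text.
3. The sponsor confirms whether *or* is intended between the two limbs. If it is, the text should make clear that a subject within the creatinine limit may enter with a clearance below 30 mL/min. If it is not, the connective needs correcting too. That is the sponsor's clinical decision.
4. The corrected criterion is applied when the per-protocol set is derived. If enrollment is complete, a documented clarification and a check of screening creatinine and clearance against the confirmed criterion would be enough.

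The cost is one word in two places, one confirmation, and a look through screening values that are already collected. No design parameter or planned table changes.
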